4.7 APACHE AND SOFA SCORES

Acute Physiology and Chronic Health Evaluation (APACHE) and Sequential Organ Failure Assessment (SOFA) scores are for patients that are admitted into the ICU. These assessments are not required for study conduct or entry but should be collected if available. The initial scores for APACHE and SOFA should be taken within 24 hours of entry into the ICU and at the time points specified in [Appendix 1a](#).

For the calculation of the initial APACHE and SOFA scores, the worst values in the first 24 hours of ICU admission should be used. SOFA scores are only for patients admitted into the ICU that have available data for calculation (i.e., partial pressure of arterial oxygen/fraction of inspired oxygen [PaO₂/FiO₂] in mmHg). See [Appendix 7](#) for SOFA score calculation.

4.8 OSELTAMIVIR MEDICATION DIARY

Patients who are discharged from the hospital with oseltamivir will be required to complete a medication diary and return the medication diary, empty (used) oseltamivir packets, and unused oseltamivir capsules to the study site at the next follow up visit.

Patients will record the date and time when each oseltamivir capsule is administered.

4.9 PATIENT, TREATMENT, STUDY, AND SITE DISCONTINUATION

4.9.1 Patient Discontinuation

Patients have the right to voluntarily withdraw from the study at any time for any reason. In addition, the investigator has the right to withdraw a patient from the study at any time. Reasons for withdrawal from the study may include, but are not limited to, the following:

- Patient withdrawal of consent at any time
- Any medical condition that the investigator or Sponsor determines may jeopardize the patient's safety if he or she continues in the study
- Investigator or Sponsor determines it is in the best interest of the patient

Every effort should be made to obtain information on patients who withdraw from the study. The primary reason for withdrawal from the study should be documented on the appropriate eCRF. However, patients will not be followed for any reason after consent has been withdrawn. Patients who withdraw from the study will not be replaced.

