4.3.2 Dosage, Administration, and Compliance

4.3.2.1 MHAA4549A and Placebo

Administration of MHAA4549A or placebo will be performed in a setting with emergency medical equipment and personnel who are trained to monitor for and respond to medical emergencies. A qualified physician or medically qualified designee will be on site during study drug administration for all patients.

A single dose of MHAA4549A or placebo will be delivered by IV infusion following dilution in 0.9% normal saline over approximately 120 minutes. Study drug should be delivered using a 0.20- to 0.22- μ m in-line filter. Compatibility testing has shown that MHAA4549A is stable when diluted in 0.9% normal saline in a polyvinylchloride bag, polyolefin bag, or ethylene vinyl acetate bag (EVA), at concentrations of 0.24 mg/mL up to 27.0 mg/mL. Study drug must be administered within the treatment window outlined in [Section 3.1.1](#). Further detailed instructions for preparation of study drug can be found in the Pharmacy Manual.

Subjects who experience a moderate-to-severe infusion-related reaction should have their infusion stopped. The infusion should not be restarted. The infusion will be discontinued in the event that the subject experiences a serious reaction and further dosing of subjects will be halted until the safety of the drug is assessed.

There are no recommended dosage modifications for MHAA4549A since it is a single infusion. Any overdose or incorrect administration of study drug should be noted on the Study Drug Administration electronic Case Report Form (eCRF). AEs associated with an overdose or incorrect administration of study drug should be recorded on the Adverse Event eCRF. General supportive measures will be taken to manage any AEs associated with overdose. Patients experiencing such AEs will be followed up clinically until the event has resolved.

Trained clinical site staff responsible for adequate and accurate study drug administration, accounting, and management will administer study drugs to patients. Study drug preparation and dosing instructions will be provided to each site. The exact times of study drug administration will be recorded in the relevant dispensing/administration logs and patient's source notes. Any noncompliance or problems with study drug administration will be recorded in the patient's source notes and reported to the Sponsor if appropriate.

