5.3.1 Adverse Event Reporting Period

Investigators will seek information on adverse events at each patient contact. All adverse events, whether reported by the patient or noted by study personnel, will be recorded in the patient's medical record and on the Adverse Event eCRF.

After informed consent has been obtained **but prior to initiation of study drug**, only serious adverse events caused by a protocol-mandated intervention (e.g., invasive procedures such as biopsies, discontinuation of medications) should be reported (see [Section 5.4.2](#) for instructions for reporting serious adverse events).

After initiation of study drug, all adverse events, regardless of relationship to study drug, will be reported until *study completion* at the Day 60 visit or *until an* Early Discontinuation visit. After this period, the investigator should report any serious adverse events that are believed to be related to prior study drug treatment (see [Section 5.6](#)).

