5.4.2.2 Events That Occur after Study Drug Initiation

After initiation of study drug, serious adverse events and non-serious adverse events of special interest will be reported until the patient *completes the study* at Day 60 or *discontinues early*. Investigators should record all case details that can be gathered immediately (i.e., within 24 hours after learning of the event) on the Adverse Event eCRF and submit the report via the electronic data capture (EDC) system. A report will be generated and sent to Safety Risk Management by the EDC system.

In the event that the EDC system is unavailable, a paper *Clinical Trial Serious Adverse Event/Adverse Event of Special Interest Reporting Form* should be completed and faxed or scanned and emailed to *the Sponsor* or its designee immediately (i.e., no more than 24 hours after learning of the event), using the contact information provided to investigators (see [Section 5.4.2.1](#)). Once the EDC system is available, all information will need to be entered and submitted via the EDC system.

Instructions for reporting post-study adverse events are provided in [Section 5.6](#).

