5.6 POST-STUDY ADVERSE EVENTS

The Sponsor should be notified if the investigator becomes aware of any serious adverse event that occurs after the end of the adverse event reporting period (defined as 60 days after the dose of study drug), if the event is believed to be related to prior study drug treatment. *These events should be reported through the use of the Adverse Event eCRF and submit the report via the EDC system. However, if the EDC system is not available, the investigator should report these events directly to the Sponsor or its designee, either by faxing or by scanning and emailing a paper Clinical Trial Serious Adverse Event / Adverse Event of Special Interest Reporting Form using the fax number or email address provided to investigators (refer to site binder).*

5.7 EXPEDITED REPORTING TO HEALTH AUTHORITIES, INVESTIGATORS, INSTITUTIONAL REVIEW BOARDS, AND ETHICS COMMITTEES

The Sponsor will promptly evaluate all serious adverse events including suspected unexpected serious adverse reactions (SUSARs) and non-serious adverse events of special interest against cumulative product experience to identify and expeditiously communicate possible new safety findings to investigators, IRBs, IECs, and applicable health authorities based on applicable legislation.

To determine reporting requirements for single adverse event cases, the Sponsor will assess the expectedness of these events using the following reference documents:

- MHAA4549A Investigator's Brochure
- Local prescribing information for oseltamivir

The Sponsor will compare the severity of each event and the cumulative event frequency reported for the study with the severity and frequency reported in the applicable reference document.

Reporting requirements will also be based on the investigator's assessment of causality and seriousness, with allowance for upgrading by the Sponsor as needed.

Certain adverse events are anticipated to occur in the study population at some frequency independent of study drug exposure and will be excluded from expedited reporting. These anticipated events include, but are not limited to, the following:

- Asymptomatic elevations of ALT, AST, and or amylase without corresponding elevations of bilirubin have been shown to be increased during influenza A infection ([Polakos et al. 2006](#); [Yingying 2011](#))
- Influenza associated disease and or complications of influenza

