Appendix 1b Schedule of *Activities*: Follow-Up Period

- If a patient is discharged prior to Day 14, he/she will need to complete the following assessments for Day 14, Day 30, and Day 60 below.
- If a patient is discharged after Day 14 but prior to Day 30, he/she will need to complete the following assessments for Day 30 and Day 60 below.
- If a patient is discharged after Day 30, but prior to Day 60, he/she will need to complete the following assessments for Day 60 below.
- If patient is hospitalized for Day 14, Day 30, and/or Day 60, please refer to Appendix 1a.

Day (D)	D14 ± 1 (If discharged BEFORE Day 14)	D30 ± 4 (If discharged BEFORE Day 30)	Day 60 ± 7 (Study Completion) or Early Discontinuation
Concomitant medications ^a	x	x	x
Vital signs ^b	x	x	x
Electrocardiogram (12-lead) ^c	x	x	x
Weight, BMI ^d	x	x	x
Adverse events	x	x	x
Hematology ^e	x	x	x
Chemistry panel ^e	x	x	x
Coagulation panel ^e	x	x	x
Urinalysis ^e	x	x	x
Flu antibodies (HAI)	x	x	x
[REDACTED]		x	x
Serum for MHAA4549A PK measurements ^f	x	x	x
[REDACTED]	x	x	x
[REDACTED]	x	x	x
[REDACTED]		x	x
[REDACTED]		x	x
[REDACTED]		x	x

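### All-cause SAE and vital-status collection to Day 60 is not required after an investigator or Sponsor withdraws a patient, and the end-of-follow-up passages disagree

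*Combined protocol and SAP*

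**What the plan says.** All references are to protocol Version 7.

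- **Leaving the study.** Section 4.9.1 lets the investigator withdraw a patient at any time. One listed reason is "Any medical condition that the investigator or Sponsor determines may jeopardize the patient's safety if he or she continues in the study"; another is the patient's best interest. The section adds: "Every effort should be made to obtain information on patients who withdraw from the study". The only outright bar on follow-up concerns consent: "However, patients will not be followed for any reason after consent has been withdrawn".
- **What is scheduled afterwards.** Section 4.9.3 asks such patients to complete one early discontinuation visit.
- **When reporting stops.** Section 5.2.1 monitors adverse events up to Day 60 or early discontinuation. Section 5.3.1 ends reporting of all adverse events at the Day 60 visit or, for those who leave early, as follows: "Early Discontinuation visit. After this period, the investigator should report any serious adverse events that are believed to be related to prior study drug treatment". Section 5.4.2.2 says "After initiation of study drug, serious adverse events and non-serious adverse events of special interest will be reported until the patient" finishes at Day 60 or leaves early.
- **Deaths.** Within the reporting period, Section 5.3.5.7 puts deaths attributed solely to influenza or related co-morbidity on the completion/discontinuation form, and all others on the adverse event form as SAEs. Deaths after the period go to Section 5.6, which covers only serious events believed related to study drug.
- **How long the period is.** Section 5.6 has it "defined as 60 days after the dose of study drug". The synopsis says all patients are followed for 60 days from dosing. Appendix 1b labels the last column "Day 60 ± 7 (Study Completion) or Early Discontinuation".
- **Endpoint and analysis.** All-cause mortality at Days 14, 30 and 60 is a secondary outcome (Section 3.3.3), summarised as a hazard ratio (Section 6.4.2). Section 6.4 censors event-free patients who are lost to follow-up when last known event-free and allows no other imputation.

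**The concern.** MHAA4549A is given once (Section 4.3.2.1: "There are no recommended dosage modifications for MHAA4549A since it is a single infusion"), with a mean half-life of about 21.5 to 23 days (Section 1.2.3). A patient withdrawn after the infusion has already been exposed. What happens to that patient up to Day 60 is still part of the mortality and safety comparison.

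Under the stop rules, continued reporting then depends on the investigator believing the event to be drug-related. In hospitalised influenza, a blinded investigator may well attribute a late death to the disease. The oversight committees are asked to look for worsening disease associated with the antibody (Section 3.1.1), and a relatedness filter is a poor way to find it. If withdrawal for a medical condition goes with a worse prognosis, censoring at withdrawal is informative and mortality is underestimated. The comparison between arms is distorted mainly if the frequency or prognosis of such withdrawals differs by arm.

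**Working it through.** **1. Tracing one patient through the text.** Suppose a patient is dosed on Day 1, withdrawn by the investigator on Day 3, and dies between Day 14 and Day 30 of what the investigator judges to be influenza.

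| Section | Consequence |
|---|---|
| 4.9.3 | One visit at discontinuation; nothing scheduled later |
| 5.2.1, 5.3.1, 5.4.2.2 | All-cause reporting ended on Day 3 |
| 5.3.5.7 | Death falls after the period, so go to 5.6 |
| 5.6, reporting rule | Not believed drug-related, so no report required |
| 5.6, definition of period | Within 60 days of dosing, so the period has not ended |
| Synopsis | Patient should be followed for 60 days |
| 4.9.1 | Effort to obtain information; no items, dates or vital-status check named |

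The first four rows leave the death without a required route. The next two say the opposite. The last permits collection without requiring it. If the death is not learned of, Section 6.4 censors the patient at about Day 3.

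**2. The last visit.** 60 − 7 = 53. The Day 60 visit may take place on Day 53. Section 5.3.1 ends the period at that visit, while Section 5.6 runs it to 60 days. No later contact is scheduled to establish Day 60 vital status.

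**3. What missed deaths could do.** The plan has no figure to reproduce here, so this is an illustration.

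- From the documents: about 110 patients per arm (Section 6.1); mortality q = 9% to 32%, from a hospital database (Section 3.2.2).
- Assumed, not in the documents: share of an arm withdrawn w = 2% to 10%; risk of death after withdrawal d = 30% to 60%; withdrawal precedes these deaths; none of them is learned of.

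Expected deaths per arm: 110 × 0.09 = 9.9 and 110 × 0.32 = 35.2.

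Deaths missed per arm = 110 × w × d. Share missed = w × d / q. Mortality estimated with censoring treated as non-informative = (q − w × d) / (1 − w).

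| q | w | d | Missed per arm | Share missed | Estimate |
|---|---|---|---|---|---|
| 9% | 2% | 30% | 0.7 | 7% | 8.6% |
| 9% | 5% | 60% | 3.3 | 33% | 6.3% |
| 9% | 10% | 60% | 6.6 | 67% | 3.3% |
| 32% | 2% | 30% | 0.7 | 2% | 32.0% |
| 32% | 10% | 30% | 3.3 | 9% | 32.2% |
| 32% | 5% | 60% | 3.3 | 9% | 30.5% |
| 32% | 10% | 60% | 6.6 | 19% | 28.9% |

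Worked line: w = 10%, d = 60%, q = 9% gives 110 × 0.10 × 0.60 = 6.6 missed; 0.06 / 0.09 = 67%; (0.09 − 0.06) / 0.90 = 3.3%.

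If d = q, the formula returns q exactly. The bias therefore comes from withdrawn patients being at higher risk than the rest; withdrawal alone does not produce it.

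**The case against.** Much can be said for the plan.

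- Section 4.9.1 concerns a condition that would make continued participation unsafe. It does not name deterioration as such. ICU admission, ventilation and death are outcomes of the trial, and ICU patients have scores scheduled to Day 60. A reader might infer that the sickest patients leave the data. The documents do not show this: withdrawal is optional, data up to the visit are kept, and no withdrawal rate is given.
- A reader might also infer that SAE collection ends altogether. It does not. Section 5.5.1 follows each recorded adverse event until it resolves or stabilises, or the patient is lost or withdraws consent. Section 5.4 requires new information on reported SAEs, including a changed outcome, within 24 hours. Drug-related SAEs stay reportable without time limit (Section 1.3.2.1).
- It is too strong to say that leaving the study after Day 1 removes observation and nothing else. Oseltamivir capsules are also an investigational product (Section 4.3.3) and run for at least 5 days.
- Sections 4.9.1 and 4.9.2 already separate leaving the study from stopping treatment. Section 4.9.2 does not send patients out of follow-up.
- Site staff are blinded, and reasons for leaving are summarised by arm (Section 6.2), so an imbalance in withdrawals would be seen.
- The study is hypothesis-generating, mortality is secondary, and further analysis detail is deferred to a SAP that is not in the pages reviewed.

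These points narrow the concern but leave a gap. Section 5.5.1 helps only if the fatal condition was already recorded as an adverse event, and Section 5.3.5.9 keeps anticipated influenza deterioration out of that record. The effort sentence in 4.9.1 draws the line at consent, which is the right place, but schedules nothing. Tabulating reasons for leaving shows who left; it does not show who later died.

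**Conclusion.** The point holds as a gap and an inconsistency. After withdrawal by the investigator or Sponsor, no passage clearly requires all-cause SAEs or vital status to Day 60. Three sections end all-cause reporting at discontinuation, while the synopsis and Section 5.6 imply 60 days. Deaths attributed to influenza after withdrawal can therefore be missed and censored. This may bias mortality at Days 14, 30 and 60 if those patients are at higher risk.

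The size cannot be stated. On the assumed ranges, 0.7 to 6.6 deaths per arm are missed against roughly 10 to 35 expected. That is 7% to 67% of deaths at 9% mortality and 2% to 19% at 32%. The upper ends combine the highest assumed withdrawal with the highest assumed risk, and the database mortality may not match a trial that excludes patients likely to die within 48 hours. With q = 32% and d = 30% the bias is negligible (estimates of 32.0% to 32.2%). None of these percentages should be read as a finding about the trial.

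The documents also do not support removing the medical-condition or best-interest grounds for withdrawal. That is a matter of clinical discretion, and the data gap can be closed without touching it. The early end of the Day 60 window is a minor part of the same inconsistency. The change is worth making because it is cheap.

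**What to change.** Leave the withdrawal grounds and the treatment-stopping rules as they are, and change data collection only.

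1. In Sections 4.9.1 and 4.9.3, state that unless consent is withdrawn, all-cause SAEs and vital status are collected to Day 60 for any patient withdrawn by the investigator or Sponsor. Telephone contact is enough; Appendix 1a already encourages telephone visits when a patient cannot attend.
2. Align Sections 5.2.1, 5.3.1, 5.3.5.7, 5.4.2.2 and 5.6 to that single period, so that a death before Day 60 has a required route whatever its attributed cause.
3. Because the last visit may fall on Day 53, require vital status to be ascertained on or after Day 60.

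The cost is protocol wording and a few telephone contacts, probably for a small number of patients. With these data collected, deaths are no longer lost for this reason.

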4.9.2 Study Treatment Discontinuation

Patients must discontinue MHAA4549A infusion and therefore treatment if they experience any of the following:

- Life threatening infusion-related reactions

Patients must discontinue oseltamivir treatment if they experience any of the following:

- Pregnancy
- Serious skin/hypersensitivity reactions

The primary reason for study treatment discontinuation should be documented on the appropriate eCRF.

The IMC and SOC may recommend to permanently discontinue dosing for all patients within one or both study arms in the event of a general safety concern.

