3.2 RATIONALE FOR STUDY DESIGN

3.2.1 Rationale for Study Design

Hospitalized influenza A infection represents a high unmet need, which, when left untreated, may progress to a more serious disease that may result in significant morbidity and mortality in otherwise healthy adults as well as in vulnerable populations.

This study is designed to estimate the improvement in outcome of a combination regimen of MHAA4549A with oseltamivir compared to a standard of care arm of placebo with oseltamivir. The study population will include hospitalized patients with influenza A requiring *ongoing* O₂ support and/or PPV support within 24 hours of hospital admission.

Study GV29216 will be a Phase 2b study involving approximately 330 patients. The sample size was determined based on an expected clinically meaningful difference of 1–2 days improvement in time to normalization of respiratory function between the control and treatment arms, assuming a 5 day median time to the time to normalization of respiratory function in the standard of care arm ([Blackwood et al. 2011](#); [Premier Inc, Charlotte, NC](#)).

This design ensures that all patients in the trial will receive the current NAI treatment, oseltamivir, as standard of care at a minimum, and will evaluate the clinical benefit of combining MHAA4549A with this standard of care regimen. Therefore, this study aims to identify a regimen that could deliver maximum benefit in this high unmet need disease, while still treating all enrolled patients with the currently accepted standard of care.

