3.2.3 Rationale for Control Group and Treatment Window

In this study, the standard of care regimen for the control or comparator group (*hospitalized influenza A patients*) is oseltamivir, an NAI. In the treatment groups, MHAA4549A will be dosed in addition to oseltamivir. *Oseltamivir* for a minimum of 5 days is permitted following treatment with MHAA4549A. Treatment for longer than 5 days is permitted based on local investigator discretion (WHO 2005; Fiore et al. 2011; CDC 2016). The oseltamivir dosing regimen is listed in Table 2. This control treatment was based on consideration of safety, ethics, and efficacy for treatment of severe influenza and is consistent with guidelines for antiviral treatment of hospitalized patients with influenza (Harper et al. 2009; Fiore et al. 2011).

Table 2 Oseltamivir Dosing Regimen

Neuraminidase Inhibitor	Dosing Regimen	Duration of Therapy
Oseltamivir	75 mg or 150 mg oral twice daily ^a	5 days ^b

^a 75 mg or 150 mg dose at the discretion of the investigator, and dose must be documented. Capsules can be opened and the granules administered via nasogastric tube, if required. For renal dose adjustments, follow local standard of care practice/local package insert and document in the eCRF.

^b Longer treatment times are at the discretion of the investigator (WHO 2005; Fiore et al. 2011; CDC 2016).

If oseltamivir resistance is highly suspected or identified or oseltamivir route of administration challenges are encountered, then following discussion with the Sponsor Medical Monitor, an alternative NAI to oseltamivir may be used. *For renal dose adjustments, local standard-of-care practice/local package insert should be followed and documented in the eCRF. Capsules other than 75 mg (for 75 mg twice a day [BID] or 150 mg BID regimens) cannot be provided through the study Interactive Voice and Web Response System (IxRS). In these instances, the study site may supply the appropriate dose and be reimbursed by the Sponsor.*

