From a safety standpoint there are no expected drug interactions between MHAA4549A, a monoclonal antibody, and any NAI, which are small molecule drugs that bind to a different viral protein than MHAA4549A. In the Phase 2a challenge study, all subjects that were dosed with MHAA4549A also received a 5-day course of oseltamivir starting on Day 7. There were no safety effects attributable to the combination when the drugs were present concurrently. *In the Phase 2a challenge study, MHAA4549A treatment did not appear to impact the exposure of oseltamivir and its active metabolite oseltamivir carboxylate. There was no suggestion of PK drug-drug interaction between MHAA4549A and oseltamivir.*

For this Phase 2b study, a combination of MHAA4549A and oseltamivir was determined to be the most clinically feasible treatment regimen, both from an ethical as well as a practical perspective. The treatment of all patients with oseltamivir ensures that all patients will receive the standard of care. Given the high morbidity and mortality of hospitalized patients with influenza A along with guidelines from Centers for Disease Control and Prevention (CDC) and Infectious Diseases Society of America (IDSA) it is recommended that NAIs are the standard of care for hospitalized patients with influenza A (Harper et al. 2009; CDC 2016). Furthermore, pre-clinical efficacy data from a study using MHAA4549A and oseltamivir in combination showed a potential synergistic effect of both compounds which may be due to the different and potentially complementary mechanisms of action, i.e. targeting viral HA and neuraminidase (NA).

Dosing of MHAA4549A is confined to a treatment window designed for best expected treatment success and to ensure that any observed effects can be attributed to the study

drug with high confidence. MHAA4549A shall only be dosed within 5 days of onset of symptoms (including fever, chills, malaise, dry cough, loss of appetite, myalgias, coryza, or nausea), no later than 48 hours after admission to the hospital, and if a subject has taken less than a total of 6 doses (3 doses for peramivir) of approved anti-influenza therapy from onset of symptoms. This proposed window is supported by data demonstrating that hospitalized influenza patients benefit from NAI treatment even at 5 days from onset of symptoms (Louie et al. 2012). The patient must start standard-of-care oseltamivir no later than 12 hours after completion of MHAA4549A administration.

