4.5.1 Permitted Therapy

Patients who use oral contraceptives, hormone-replacement therapy, or other maintenance therapy should continue their use.

All therapies required for management of the patient's acute illness are permitted except for those listed below in [Section 4.5.2](#).

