4.5.2 Prohibited Therapy

Use of the following therapies is prohibited during the study and for at least 7 days prior to study treatment, unless otherwise specified below: probenecid, amantadine, or rimantidine.

Use of other NAIs, including but not limited to oseltamivir, zanamivir, *laninamivir*, and peramivir, are prohibited during the study, but allowed up to a total of 6 doses (3 doses for peramivir) in the period from onset of symptoms and prior to study treatment as outlined in the exclusion criteria. Patients must start standard-of-care oseltamivir no later than 12 hours after completion of MHAA4549A administration. If oseltamivir resistance is highly suspected or identified or if oseltamivir route of administration challenges are encountered then, following discussion with the Sponsor's *Medical Monitor*, an alternative NAI to oseltamivir may be used.

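### Oseltamivir must be stopped after a serious skin or hypersensitivity reaction, but no section authorizes a replacement neuraminidase inhibitor (NAI) for that reason

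*Combined protocol and SAP*

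**What the plan says.** All references are to the Version 7 protocol.

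- **Section 4.9.2 (stopping).** "Patients must discontinue oseltamivir treatment if they experience any of the following". The triggers are pregnancy and "Serious skin/hypersensitivity reactions". The section asks for the reason to be recorded and says nothing about replacement antiviral therapy.
- **Section 4.5.2 (prohibition).** Other NAIs "are prohibited during the study, but allowed up to a total of 6 doses (3 doses for peramivir") in the window between symptom onset and study treatment.
- **Section 4.5.2 (exception).** "If oseltamivir resistance is highly suspected or identified or if oseltamivir route of administration challenges are encountered then", after discussion with the Medical Monitor, an alternative NAI may be used.
- **Section 3.2.3 (exception repeated).** The same two conditions: "If oseltamivir resistance is highly suspected or identified or oseltamivir route of administration challenges are encountered".
- **Section 4.5.1 (general permission).** "All therapies required for management of the patient's acute illness are permitted except for those listed below in" Section 4.5.2.
- **Sections 3.2.1 and 3.2.3 (rationale).** "This design ensures that all patients in the trial will receive the current NAI treatment", and "it is recommended that NAIs are the standard of care for hospitalized patients with influenza A".
- **Section 3.1.1 (course length).** Oseltamivir is to be given for at least 5 days, stated as 10 doses.

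**The concern.** Read together, these rules require a site to stop oseltamivir for a serious reaction and then give it no permitted way to continue NAI treatment. The patients are hospitalized with influenza A and need oxygen or positive pressure ventilation, and the protocol itself names NAIs as their standard of care.

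The stop is compliant; only the switch is not. The site must either leave the course incomplete or give another NAI and record a deviation. In the second case, a clinically expected action is counted among the deviations that Section 6.2 summarizes by treatment group. What is at stake is patient care and the protocol's consistency with its own rationale, not the validity of an estimate.

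**Working it through.** The plan gives no figure on this point, so the check is a comparison of text.

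**1. Set the two lists side by side.**

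| Reason | Oseltamivir must stop (4.9.2) | Alternative NAI permitted (4.5.2, 3.2.3) |
|---|---|---|
| Serious skin or hypersensitivity reaction | Yes | No |
| Pregnancy | Yes | No |
| Resistance highly suspected or identified | Not listed | Yes |
| Route-of-administration challenges | Not listed | Yes |

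No row has Yes in both columns. Pregnancy has the same gap, but it is very unlikely to matter, because a negative test is required within 2 days before study drug.

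**2. Look for another provision that permits the switch.**

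- Section 4.5.1 allows treatment of the acute illness but excepts whatever Section 4.5.2 lists, so it does not reopen other NAIs.
- An allergic reaction is not naturally a route-of-administration problem. The difficulty is the drug, not how it is delivered.
- The entry exclusion in Section 4.1.2 removes known oseltamivir hypersensitivity. It cannot prevent a first reaction on study, which Section 4.9.2 anticipates.
- The Medical Monitor discussion applies once one of the two listed conditions is met. It is not a separate discretion.
- Section 9.2 provides for documenting and explaining a deviation. That lets a site act, but the switch is still a deviation.

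**3. See how the list has been handled.** The summaries of changes show that Version 5 added the route condition and that Version 7 widened the resistance condition by removing its limit to the treatment period. The sponsor has amended this sentence when it wanted more cases covered, and hypersensitivity has not been added.

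**4. Size for one patient.** The minimum course is 5 days × 2 doses per day = 10 doses (Section 3.1.1). After k on-study doses, the doses with no authorized NAI replacement number 10 − k:

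| Doses taken before the stop (k) | Doses left (10 − k) |
|---|---|
| 1 | 9 |
| 2 | 8 |
| 4 | 6 |
| 9 | 1 |

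Up to 6 NAI doses (3 of peramivir) may have been given before study treatment. The result is therefore an incomplete course, not an absence of treatment.

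**The case against.** The strongest objection is that the prohibition is too loosely drafted to be read strictly. Section 4.5.2 names oseltamivir, the mandated background drug, among the prohibited other NAIs, so the sentence cannot be applied literally. It could be read as aimed at NAI use beyond the background drug, not at replacement after a required stop. The exception says when an alternative may be used; that these are the only cases is inferred from the prohibition. The drafting flaw is real, but the ordinary reading is still that other NAIs are barred outside the two stated cases.

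The second objection is that no patient is actually denied care:

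- Section 4.9.1 allows withdrawal in the patient's best interest, after which Section 4.5.2 no longer applies.
- Section 8.1 commits the study to Good Clinical Practice and the Declaration of Helsinki, or to local law where that protects the patient more.
- Section 9.6 exempts changes needed to remove an immediate hazard from prior approval.
- A deviation can be documented.

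These routes do let a site treat the patient. None makes the switch permitted on study, and withdrawal costs follow-up.

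The third objection is about weight, and most of it stands. Sections 6 and 6.4 define the efficacy population by randomization and central PCR confirmation and analyze patients as randomized, so a switch would neither remove a patient nor alter an estimate. The number affected is unknown. The 10 − k count describes the unfinished course and says nothing about frequency or clinical effect. It is also fair that a safety stop in an individual is a normal exception to a design statement about all patients. The gap is the missing authorization for what follows the stop.

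**Conclusion.** The concern holds, at minor severity. Following the written rules, a patient who must stop oseltamivir for a serious skin or hypersensitivity reaction has no authorized NAI for the rest of the course while on study.

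Per patient this is 1 to 9 of the 10 minimum doses. Across the trial the number of patients is probably small and cannot be estimated from the documents. Power, sample size and the analyses are unaffected.

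The conclusion rests on reading the Section 4.5.2 prohibition in its ordinary sense, and on taking the two listed exceptions as the only ones.

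**What to change.** In the alternative-NAI sentence of both Section 4.5.2 and Section 3.2.3, after the route-of-administration condition, add: *or if oseltamivir must be discontinued under Section 4.9.2*. Keep the discussion with the Medical Monitor. In Section 4.9.2, add: *For alternative NAI treatment after oseltamivir discontinuation, see Section 4.5.2.* The clause covers both Section 4.9.2 triggers and leaves the choice of agent to the physicians.

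The cost is one clause in two sections and one cross-reference, with no added patients, procedures or eCRF fields. A few patients would receive a background NAI other than oseltamivir, which the protocol already accepts for resistance and route problems.
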